6.10.3 Analysis of Endpoints

The schedule of assessments for efficacy parameters is described in Section 6.6.8 *Schedule of Evaluation*. All data will be entered in the case report form and will also be entered into a secure electronic subject chart used at the University of Illinois at Chicago (PowerChart by Cerner, Missouri, USA). All correspondences, blood work and examinations are automatically recorded in PowerChart.

All subjects who receive an islet transplant will be analyzed on an intent to treat basis. Subjects not tolerating exenatide or any other study medication and completing the study will be included for endpoint analysis. Descriptive information on subjects who withdraw from any study medication will be provided; it is unlikely that the study would have enough statistical power to allow for a subset analysis.

We plan to recruit and transplant all subjects within the first three years of this study and to complete all sequential transplants and follow-up by the end five years. All subjects will have a minimum follow-up of one year after the completion of islet transplantations. All subjects will be offered a 5-year follow-up.

6.11 Monitoring of Patient Safety

6.11.1 Informed Consent

The investigator is responsible for obtaining informed consent from all subjects in accordance with U.S. federal regulations (21 CFR 50 and 21 CFR 312.60) (see

Appendix *Letter of consent*). An individual meeting with each subject will give detailed information about the purpose, risks, and comforts involved and potential benefits of the study. The subject will be involved an explanation and discussion of the contents of each page of the consent form to ensure understanding of the consent form.

The subject will sign and date a written Informed Consent. The original signed and dated copy of the Informed Consent will be maintained at the study site. The names of the subjects enrolled during this study will be considered confidential.

6.11.2 Patient Eligibility and Safety

Data Monitoring Committee

In order to assist in the monitoring of the safety of subjects participating in this study, the investigator will establish a Data Monitoring Committee (DMC). The DMC will consist of 3 members who have training in medicine and/or organ transplantation. Some members may provide temporary coverage for the investigator or co-investigator while they are off-site (e.g., vacation) but otherwise will not be involved in the medical care of subjects. In the event that a DMC member is covering an investigator, that member will reclude him/herself from voting on DMC decisions. At all times, only one member may cover an investigator at a time so that 2 members are available for review of safety data and to make any decisions.

For each subject, the DMC will review the eligibility and safety data approximately 2 weeks following each islet cell transplantation. In the event that a second transplantation will be done in the same subject during the first 2 weeks following the first transplantation, the DMC will review the eligibility and available safety data for this subject prior to his/her second transplantation. The DMC must review the safety data through week 2 following transplantation on the preceding subject and agree that islet cell transplantation can continue in the subsequent subject. In this way, an interval of 2 or more weeks will exist between subjects undergoing islet transplantation to allow the review of safety events. This applies to the first 2 subjects in this cohort. If no serious events were observed, subsequent transplants can be performed in another patient during this 2-week review phase following a transplant.

The DMC will meet every 3 months to review the collected clinical data in order to assess safety. The DMC may also meet in an emergency situation when requested by the investigators or should the study meet a stopping rule (See Section 6.10.6).

It should be noted that in addition to the formal monitoring of safety by the DMC, the IRB will be notified of each serious adverse event. As described above, the IRB has the right to suspend the clinical study at any time for safety reasons.

Subject Eligibility

Only subjects fulfilling the inclusion criteria and not presenting any of the exclusion criteria will be entered into the study. The inclusion and exclusion criteria will be evaluated by the principal investigator, [name]. Fulfillment of eligibility criteria will be reviewed by the DMC (see above) and the study monitor (see Section 6.13.2).

6.12 Regulatory Standards

6.12.1 Case Report Form

A case report form (CRF) will be completed for every subject who signed a written Informed Consent form and undergoes an islet cell transplantation..

The principal investigator must sign and date a case report certification statement upon completion of the study by the subject. This signature will indicate that thorough inspection of the data has been made and will certify the contents of the case report forms.

The investigator or institution will retain all original source documentation (e.g., laboratory results, treatment records, audit queries, etc.) unless specified otherwise by the protocol. All data will be entered in the study chart and will also be entered into a secure electronic patient chart used at the University of Illinois at Chicago (PowerChart by Cerner, Missouri, USA). All correspondences, blood work and examinations are automatically recorded in PowerChart, which is protected by HIPAA. The results as they become available will be entered on the appropriate case report forms.

Case report forms will be reviewed at the study site by a clinical monitor who will make a decision as to their acceptability in regard to completeness and accuracy of data recording. Audit queries will be generated for omissions, corrections, and clarifications.

[figure not shown]
A copy of the Transplant Release Form containing all the relevant information on the islet graft characteristics, unique batch identification number and compliance with the release criteria will be included in the case report form. There is traceability in all steps of the transplant procedure and adverse event reporting, which will respect the mutual anonymity of the donor and the recipient. The traceability system with inclusion of the UNOS donor identification number enables the path taken by each donation to be traced from the donor to the recipient or to disposal and vice versa.

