6.8.3 Follow-Up for Subjects Withdrawn from Treatment

Subjects will be followed on an intention-to-treat basis; data from all enrolled subjects who are assigned a participant identifier and who undergo islet transplantation will be collected, irrespective of outcome, for the scheduled minimum follow-up period of one year.

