6.9 Adverse Events Definitions and Monitoring

6.9.1 Adverse Event (AE)

An adverse event is any unfavorable and unintended diagnosis, symptom, sign (including an abnormal laboratory finding), syndrome, or disease which either occurs during the study, having been absent at baseline, or if present at baseline, appears to worsen.

The length of time between screening and first transplantation may be 6 months or more. Therefore, non-serious adverse events will be recorded on the case report forms (CRF) for the period starting with hospitalization for the first transplantation and during the subsequent study period because these events are relevant to the islet cell transplantation. All serious adverse events (see below) regardless of time relative to transplantation will be recorded on the case report form

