#### **4. ANALYSIS POPULATIONS**

**ITT population:** Any patient in whom protocol-directed therapy (e.g., pre-transplant immunosuppression) is initiated will be included in the Intent-to-treat (ITT) population. All efficacy analyses will be on this ITT population regardless whether transplantation occurs or not.

**Safety Population:** Any patient in whom protocol-directed therapy is initiated will be included in the Safety population, which is the same as the ITT population. Patients in this population might not receive an islet transplant. All safety analyses will be on this Safety population.

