#### **5. PATIENT ACCOUNTABILITY**

The disposition of patients will be summarized for all patients entered in the clinical database. The following disposition information will be summarized:

- The number and percent of patients who completed the study and the number and percent of patients who were withdrawn;
- The number and percent of patients withdrawing by reason for withdrawal;
- The number and percent of patients not reaching 1 year post first transplant henceforth determined ongoing as of April 13, 2015 and
- The number and percentage of patients included in the Intent-to-treat populations.

All percentages will use the number of patients entered into the database as the denominator. In addition, a data listing of patients withdrawn will be provided and will include for each patient: demographics (age and race), day of withdrawal relative to day of study medication, concomitant medications taken, and reason for withdrawal.

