#### **9.1.2. Treatment of Missing Data**

The primary endpoint should be evaluable for all patients in the ITT population. However missing data can occur due to death, if the patient withdraws consent to be followed, or if immunosuppression is begun but the patient never receives a transplant. In these cases the endpoint will be classified as failure to achieve a favorable outcome. Should the endpoint not be evaluated for a patient for other reasons, a failure will be imputed unless data available at a time longer than one year after transplant indicates otherwise, in which case, that later value will be imputed.

All imputations will be reported in a patient data listing along with the reasons for imputation. The rates and the exact 95% confidence intervals for complete data and imputed data will be compared to ascertain the sensitivity of the imputation.

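### The protocol's CRF, follow-up and analysis rules stop at transplanted subjects, so they do not guarantee capture of the never-infused patients whom the SAP counts as failures

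*Protocol*

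**What the plan says.** Three protocol rules stop at the transplanted subject:

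- Section 6.12.1: a CRF is "completed for every subject who signed a written Informed Consent form and undergoes an islet cell transplantation".
- Section 6.8.3: "data from all enrolled subjects who are assigned a participant identifier and who undergo islet transplantation will be collected", for a minimum of one year.
- Section 6.10.3: "All subjects who receive an islet transplant will be analyzed on an intent to treat basis".

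The SAP uses a wider set. Section 4 admits to the ITT and Safety populations any patient in whom protocol-directed therapy has begun, and adds: "All efficacy analyses will be on this ITT population regardless whether transplantation occurs or not". Section 9.1.2 scores as a failure the case "if immunosuppression is begun but the patient never receives a transplant". Section 2.9, which lists departures from the protocol's planned analysis, does not mention the change of population.

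The protocol's own adverse-event rules also reach further than 6.12.1. Section 6.9.1 states: "All serious adverse events (see below) regardless of time relative to transplantation will be recorded on the case report form". Sections 6.9.1 and 6.9.5 also put non-serious events on the CRF from admission for the first transplant, which is before infusion.

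**The concern.** The primary analysis is one proportion in a single-arm trial intended to support a licence application, so its denominator matters. The SAP's denominator includes patients who start therapy and are never infused. The protocol's data rules do not require a CRF or follow-up data for them, apart from adverse events under 6.9.1 and 6.9.5. SAP 5 builds disposition from the database ("The disposition of patients will be summarized for all patients entered in the clinical database"), and SAP 3.1 draws the listings from it too. A patient without a CRF may therefore be missing from disposition, ITT and Safety.

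Every such patient is a failure by rule. Leaving one out shrinks the denominator and leaves the numerator unchanged, so the error runs in one direction. The safety record is exposed as well, because events before an infusion that never happens have no assured place in the tables.

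**Working it through.** **1. Can the case arise?** Yes. Protocol 6.5.2 and 6.5.4 give induction and other protocol drugs before infusion. Protocol 6.5.1 makes a raised portal pressure, confirmed at the start of the procedure, a contraindication to continuing. SAP 4, 8.2.1, 8.2.2 and 9.1.2 all provide for patients with no transplant.

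**2. What each rule does with a patient who starts therapy and is never infused**

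| Rule | Treatment of that patient |
|---|---|
| Protocol 6.12.1 (CRF) | Not among those for whom a CRF is required |
| Protocol 6.8.3 (follow-up data) | Not among those whose data are to be collected |
| Protocol 6.10.3 (analysis) | Outside the intent-to-treat analysis |
| Protocol 6.9.1, 6.9.5 (adverse events) | Events to be entered on the CRF |
| SAP 4 | In ITT and Safety |
| SAP 9.1.2 | Failure |
| SAP 2.9 | Difference not listed |

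The protocol disagrees with the SAP, and 6.12.1 disagrees with 6.9.1 and 6.9.5.

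**3. Do the safety tables have a place for them?** SAP 10.1.1 starts the treatment-emergent window at the first islet infusion, and SAP 10.1.5 limits all tabular adverse-event summaries to treatment-emergent events. The transplant-count strata in the shells for Tables 14.3.1 and 14.3.6 run over 1, 2 and 3 transplants, with none for zero. A CRF alone would not bring these patients' events into the tables.

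**4. The plan's own precision figure.** Protocol 6.10.2 and SAP 2.8 assume 80% success. The half-width is 1.96 × √(0.8 × 0.2 / n):

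- n = 50: 0.1109 (stated ±0.111)
- n = 40: 0.1240 (stated ±0.124)

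Both reproduce and are not in dispute.

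**5. Effect of omission.** Let x be the successes among n infused patients and k the number who started therapy but were never infused. The SAP 4 rate is x/(n + k). If the k patients are missing from the database, the reported rate is x/n, which is larger whenever k > 0 and x > 0. Intervals are exact two-sided 95% (Clopper-Pearson), as in SAP 9.1.1. The value of k is an assumption, because the documents give none.

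| Scenario | k | Rate | Exact 95% CI |
|---|---|---|---|
| 50 infused, 40 successes | 0 | 40/50 = 80.0% | 66.3-90.0 |
| | 1 | 40/51 = 78.4% | 64.7-88.7 |
| | 2 | 40/52 = 76.9% | 63.2-87.5 |
| 15 infused, 12 successes | 0 | 12/15 = 80.0% | 51.9-95.7 |
| | 1 | 12/16 = 75.0% | 47.6-92.7 |

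The 15-patient case is in SAP 2.8, which claims 88% power there at an observed 80%. At n = 50, one omitted patient moves the estimate by 80.0 - 78.4 = 1.6 points. At n = 15 it moves by 80.0 - 75.0 = 5.0 points.

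The SAP's minimal difference of 50 points over a standard-treatment rate of 0.3% (SAP 2.7.2) to just under 1% (SAP 2.8) implies a benchmark of 50.3% to just under 51%. The lower limit is above that range at 12/15 (51.9%) and below it at 12/16 (47.6%). SAP 9.1.1 ties no success rule to this interval, so the comparison shows sensitivity only.

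**The case against.** A reader might infer that these patients cannot be counted as failures at all. The documents do not support that. Failure under SAP 9.1.2 is assigned by rule and needs no HbA1c, hypoglycemia or follow-up data, only evidence that therapy began and no infusion followed. Protocol 6.12.1 keeps all data in the study chart and electronic chart, and 6.12.4 requires a screening log and a list of participant names and codes. The patients can be identified.

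A reader might also infer that data are collected only from infused subjects, and that serious events in the others vanish. Section 6.12.1 says for whom a CRF will be completed; it does not forbid one for anyone else. Sections 6.9.1 and 6.9.5 call for adverse events on the CRF before infusion. Protocol 6.11.2 has the IRB notified of each serious event, and 6.9.5 sends reportable ones to the FDA, IRB and monitoring committee. The SAP was written after review of the CRF (SAP 1), and the Table 14.1.1 shell is headed for all enrolled patients. The authors expected some data on non-transplanted patients.

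The route is also narrow. Under 6.5.1 the subject goes to the radiology suite only after product release and a negative crossmatch, and failed portal access leads to a surgical approach. At n = 50, about 1.5 points per patient is small beside a half-width of about 11.

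All of this limits the size and makes repair easy. It does not remove the gap. No rule moves a never-infused patient from chart or log into the database, and the adverse-event rules would not create a record of treatment start or disposition for a patient without an event.

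**Conclusion.** The contradiction holds in the text. Protocol 6.12.1, 6.8.3 and 6.10.3 define a transplanted-only set, SAP 4 and 9.1.2 define a wider one, SAP 2.9 does not declare the change, and 6.12.1 conflicts with 6.9.1 and 6.9.5. The supported conclusion is that capture of the SAP's ITT population is not guaranteed. It is not that capture is impossible or that patients have been lost.

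If any are omitted, the success rate can only be too high: by 1.6 points for one patient and 3.1 for two (80.0 - 76.9) at 40/50, and by 5.0 points for one at 12/15. If no patient starts therapy without being infused, the effect is zero. These sizes rest on an assumed k and on the plan's expected 80% success among the infused. The correction should be made because the bias has a known direction and the remedy is inexpensive.

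**What to change.** - **Protocol 6.12.1:** complete a CRF for every subject from the start of protocol-directed therapy, covering at least treatment start, disposition and adverse events. Add an SAE record for any consented subject with a serious event, so that 6.9.1 can be met.
- **Protocol 6.8.3 and 6.10.3:** use the SAP 4 population.
- **SAP 2.9:** list the change of analysis population.
- **Reporting:** give the number of patients who started therapy and were never infused, even if zero. Complete their CRFs retrospectively from the charts and screening log.
- **SAP 10.1.1 and 10.1.5:** start the treatment-emergent window at the first protocol-directed therapy, or tabulate pre-infusion events separately. Add a no-transplant category to the adverse-event shells.

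A full CRF for everyone at consent is not needed. Consent is signed in screening phase 1 (protocol 6.6.2), so that would add every screen failure and wait-listed subject.

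The cost is wording in both documents, minor extra data entry from records already held, and possibly a slightly lower success rate.

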6.12.2 Clinical Monitoring of the Study

The study will be monitored in compliance with the relevant parts of 21 CFR and according to ICH GCP Guidelines.

[figure not shown]
The following organizational chart depicts the principal investigator's oversight of the clinical study:

Organizational Chart

Study Conduct (Site)

An independent monitor knowledgeable in Good Clinical Practice (GCP) guidelines and regulations will monitor the clinical study and report to [name].

The monitor will visit the study site prior to study initiation and periodically thereafter to monitor the acceptability of the facilities, the agreement between CRF entries and original source documentation, adherence to the clinical protocol including documentation of study procedures and adherence to the treatment plan, adherence to GCP and to applicable FDA regulations, and the maintenance of adequate clinical records. The monitor will also verify documentation of informed consent and study eligibility for all subjects enrolled. The monitor will review all CRFs to verify that data are recorded appropriately including any changes and corrections to the CRF. The monitor will have access to participant records, medication sheets, laboratory data, and other source documentation.

In addition to the initiation visit, the clinical site will be monitored yearly during the study and at study completion or termination. Monitoring visits during the study conduct may occur after the 2nd and 5th subject have received their first islet cell transplantation. The investigator may increase the number or change the timing of these visits depending upon the occurrence of safety events. At each visit, the investigator will cooperate with the monitor in their review and verification of all CRFs. The monitor will ensure that all required safety reports are submitted to FDA and IRB within the required timeframes. The monitor will also ensure that any study protocol modifications/amendments are submitted to FDA and IRB as required.

All information contained in a subject's CRF must have corresponding source documentation. This source documentation includes but is not limited to notes taken at study visits recording the date of the visit, vital signs, physical findings, adverse events, and concomitant medications; laboratory reports; hospital records; and clinic records. Any correction of errors in the CRF will be first reviewed with the investigator prior to correction. The reason for any correction to the CRF will be noted along with the date and initials of the person making the correction.

The records of the subject may be audited by the FDA. The investigator agrees to allow access to the required subject records in the event of such an audit.

Within a reasonable time following completion of the study, a final study report will be written and submitted to FDA.

6.12.3 Study Subject Confidentiality

The medical and research record will be confidential to the extent permitted by law. Some of the research information will be part of the subject's permanent medical records. Study subjects will be identified by a code for the research records, and personal information from research records will not be released without written permission by the subject except:

- If necessary to protect the subject's rights and welfare (for example, if the subject is injured and needs emergency care or when the UIC Institutional Review Board monitors the research or consent process)
- If required by law

In compliance with regulatory guidelines regarding the monitoring of clinical studies, it is required that data generated as a result of the study be available for inspection on request by the study monitor and regulatory agencies. These shall include all study-relevant documentation, including medical histories to verify eligibility, laboratory test results to verify transcription accuracy, treatment and diagnostic reports, admission/discharge summaries for hospital admissions occurring while the subject is on-study, and autopsy reports (if available) for deaths occurring during or in temporal proximity to the study.

The subject will not be identified in any publication about this study. However, the FDA, IRB, and the investigators of the study at UIC may review the records, and as a result the subject's name will be seen. However, the persons reviewing the record will be bound to the rules of confidentiality and will not reveal the identity to others.

As part of the required content of the informed consent, all subjects will be asked for consent for access to the subject's medical record by the study monitor, FDA, and IRB.

6.12.4 Records

The FDA requires that an investigator retain records for a period of 2 years following the date a New Drug/Biologic Application or Product License Application is approved for the drug for the indication for which it is being investigated; or, if no application or license is to be filed, or if the application or license is not approved for such indication, until 2 years after the investigation is discontinued (21 CFR 312.62).

The investigator will ensure that the following records are maintained: subject files containing copies of completed case reports and supporting documentation and a copy of the signed, Informed Consent form.

Investigator files will include copies of the executed form FDA 1572, Curricula Vitae for the principal investigator and co-investigators, copy of the IRB approval of the protocol **and Informed Consent forms, copies of correspondence with IRB and FDA, protocol and** protocol amendments, revisions to the Informed Consent, documentation of the composition of the IRB, normal values with ranges for medical, laboratory, and technical procedures and tests included in the protocol, certification or accreditation of laboratories used, all monitoring reports, log of subject screening for eligibility, list of

participant names and codes, signature sheet for all persons authorized to make entries and/or corrections on the CRF, documentation of location and identification of any retained samples of body fluids.

